5.2 Follow-up Visits (M2 to M18)

Follow-up consultations with a nephrologist or hospitalizations will be performed at months 2, 4, 6, 9, 12, 18 and 24 from D0.

A two days hospitalization with mGFR, serum creatinine and proteinuria evaluation and repeat renal biopsy will be performed at month 12. Only one day hospitalization is scheduled if biopsy is not performed, or only one consultation is scheduled if biopsy is not performed and mGFR is not measured.

A one-day hospitalization with mGFR, serum creatinine and proteinuria evaluation will be performed at month 24. Only one consultation is scheduled if mGFR is not measured.

At each consultation (M2, M4, M6, M9 and M18) or hospitalization (M12 and M24) will be performed:

- Medical interview evaluating compliance for treatments and lifestyle recommendations

- Clinical examination with sitting blood pressure measurement, checking for postural hypotension, weight measurement, general and cardiovascular examination, and ethnic origin.

- Biochemistry: plasma sodium, potassium, albumin, total proteins, bicarbonate, chlorure, fasting glycemia, total and LDL cholesterol, triglycerides, urea, uric acid, serum creatinine (enzymatic IDMS-traceable assay), C reactive protein. Urinary protein, creatinine, sodium and urea will be evaluated on a 24-hour urinary collection (or urinary sample except to M2 and M4), eGFR.

- Haematology: blood count.

Biochemistry and haematology analyses are associated with care so they can be obtained before the consultation from private practice laboratories.

- at the visit M12 and M24, SF36 scale and biological collection (blood and urine)

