4.1.2 Secondary assessment criteria

Failure at 6 months will be defined as:

- PCR > 0.75 g/g
- or PCR > 0.5 g/g and > 30% of initial PCR
- or eGFR < 80% of initial eGFR
- or ESRD
- or renal transplantation
- or death.

Failure at 12 months will be defined as:

- PCR > 0.75 g/g
- or PCR > 0.5 g/g and > 30% of initial PCR
- or mGFR < 80% of initial mGFR (or eGFR if unavailable)
- or ESRD
- or renal transplantation
- or death.

Histological lesions evolution at 12 months :

The evolution of histological lesions will be assessed as the proportion of patients of both therapeutic groups with persistent severe histological lesions in repeat kidney biopsy at 12 months.

GFR evolution (mGFR or eGFR if unavailable):

The evolution of GFR at 12 and 24 months will be assessed as:

- the absolute value of GFR
- the absolute difference of GFR from the baseline
- the annual degradation (ml/min/1,73m²/year) of GFR during the 24 months

Proteinuria evolution

The evolution of proteinuria will be assessed as:

- the absolute value of proteinuria at 12 and 24 months
- the absolute difference of proteinuria from baseline at 12 and 24 months

Identification of prognosis markers of failure at 24 months:

Clinical, histological, and biological data (including PCR ratio, eGFR and mGFR, renal histological lesions) will be compared between patients with or without failure.

Comparison of side effects in each therapeutic group.

Comparison of life quality scale in each therapeutic group with SF36 scale at 12 and 24 months

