5.3 End of research visit (M24)

The last visit is scheduled at month 24 from first GFR measurement, during a one-day hospitalization with mGFR, serum creatinine and proteinuria evaluation at the same exams as in the previous visits.

Expected length of participation and description of the chronology and duration of the research.

Maximum	period	between	selection	and	15 days min

inclusion Inclusion period The included subjects' length of participation:	24 months
Treatment period:	4 months
Follow-up period:	24 months+ 21 days max
Total research period:	48 months

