5.4 Table or diagram summarising the chronology of the research

Actions	Inclusion	D0	M2 M4	M6 M9	M12	M18	End of research M24
Visit	Consultation*	hospitalization*	consultation	consultation	hospitalization**	consultation	Hospitalization***
History	Х						
Clinical exam, Medical Interview	x	х	x	x	x	x	х
Inclusion/ Exclusion criteria	x						
Informed consent, randomization	x						
Measured GFR (or estimated)		х	eGFR	eGFR	x	eGFR	Х
Tests (biochemistry, haematology)		х	Х	x	х	x	х
Biological collection (blood, urine)****	X(if control group and mDFG not available)	х			x		x
Sample for PK (5ml)		X (D0,D1,D2)	Х				
Dispensation of treatments		X	X (M2)				
Renal biopsy					Х		
SF36 scale					Х		X
Compliance CT		X	Х				
Compliance RAS	Х	X	X	X	Х	Х	X

Adverse	×	×	×	Y	×	Y
events	~	~	^	^	~	^

* D0: for the control group, 1 one-day hospitalization (= 1 HDJ) if mDFG is available or only consultation (= inclusion/randomisation visit) if mDFG is not available and for the experimental group 3 one-day hospitalizations (=3 HDJ)

** 2 days hospitalization (= 2HC) if biopsy is perfomed and 1 one-day hospitalization (1 HDJ) if mGFR is measured, or only 1 consultation if biopsy is not perfomed and mGFR is not measured

1 one-day hospitalization (= 1 HDJ) or only 1 consultation if mGFR is not measured * DNA sample will be obtained from one of blood samples of biological collection at D0 for control group.

During the first year, the delay accepted to organise every visit is ± 1 week. During the second year, the delay accepted to organise every visit is ± 1 month.

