7.4.1. Authorised rescue medication in the control group

In the control group, atM2, corticosteroid treatment (4 months of treatment, same protocol of experimental group) should be administred in case of rapid deterioration of renal function (i.e. eGFR (CKD-EPI formula) is < 70% of initial eGFR). Before corticosteroid administration, eGFR will be re-evaluated on a second sample, within an interval of at least 14 days.

At 4 months, rescue corticosteroid treatment (4 months of treatment, same protocol of experimental group) could be administred in case of failure defined by:

- PCR > 0.75 g/g
- or PCR > 0.5 g/g and >30% of initial PCR
- or eGFR (CKD-EPI formula) < 80% of initial eGFR,

In case of failure, before corticosteroid administration, proteinuria and eGFR will be reevaluated on a second sample, within an interval of at least 14 days.

At 6, 9, 12, or 18 months, rescue corticosteroid treatment (4 months of treatment, same protocol of experimental group) should be administred in case of failure defined by:

- PCR > 0.75 g/g
- or PCR > 0.5 g/g and >30% of initial PCR
- or eGFR (CKD-EPI formula) < 80% of initial eGFR,

In case of failure, before corticosteroid administration, proteinuria and eGFR will be reevaluated on a second sample, within an interval of at least 14 days.

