10.5 Period for notifying the sponsor

The investigator must report all SAE that occur in research subjects:

- After the date of the first procedure specific to the research

- Throughout the period during which the participant is monitored, as determined by the research

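### Follow-up visits run from D0, so a control rescued at M12 or M18 can take the whole 4-month steroid course between two scheduled visits, and an M18 rescue has only about 1.5 months of observation afterwards

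*Protocol*

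**What the plan says.** - **Calendar.** Protocol 5.2: "Follow-up consultations with a nephrologist or hospitalizations will be performed at months 2, 4, 6, 9, 12, 18 and 24 from D0". Examination, blood pressure, biochemistry including fasting glucose and potassium, and blood count belong to each of these visits. The 5.4 table adds adverse events.
- **Rescue.** Protocol 7.4.1, control group: "At 6, 9, 12, or 18 months, rescue corticosteroid treatment (4 months of treatment, same protocol of experimental group) should be administred". The failure must first be re-checked "on a second sample, within an interval of at least 14 days". No maximum interval is given.
- **Windows.** Protocol 5.4: "During the first year, the delay accepted to organise every visit is ± 1 week" and "During the second year, the delay accepted to organise every visit is ± 1 month".
- **Steroid-specific rows of the 5.4 table.** Dispensation is marked at D0 and M2, and steroid compliance at D0 and M2/M4. Nothing is marked for a rescue course.
- **End of follow-up.** Protocol 5.3 gives "24 months+ 21 days max", with no extension for rescued patients.
- **Event reporting.** Protocol 10.5 has serious events reported "Throughout the period during which the participant is monitored, as determined by the research". Section 10.3 requires all adverse events, serious or not, in the case report form. Section 10.4 follows known events to resolution, even after the patient has left the trial.
- **Use of the data.** Protocol 4.1.2 lists "Comparison of side effects in each therapeutic group" among the secondary criteria, and 9.2 analyses toxicity by treatment received.

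**The concern.** The regimen can start at several points in the control arm, but the visits that examine patients and draw bloods are fixed to D0. The question is whether each permitted rescue course meets at least one of those visits.

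If a course meets none, raised blood pressure, glucose or potassium changes and blood-count changes during treatment are found only if the patient reports something or local care happens to look. Protocol 10.3 itself names severe hypertension, diabetes, infection and fracture among the relevant harms. It also exempts headache and leg oedema from immediate notification except in the first 2 months of corticotherapy, and a late-rescued control would have no follow-up visit in those 2 months.

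The drafters did tie pharmacokinetic sampling to rescue treatment (3.3), but tied no safety assessment to it. Protocol 5.5 counts corticosteroids as added by the research, and the care samples it lists fall on the same D0-based months, so the document does not hand this monitoring over to routine care.

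**Working it through.** The plan gives no figure of its own for this point, so there is none to reproduce. The check is calendar arithmetic.

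**Inputs.** Visits at M2, 4, 6, 9, 12, 18 and 24 (5.2); course of 4 months after a repeat sample at least 14 days later (7.4.1); windows of ±1 week in year 1 and ±1 month in year 2 (5.4). Conversion: 14 / 30.44 = 0.46 month.

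**Formulae.** Start = trigger visit + 0.46. End = start + 4. Remaining follow-up = 24 − end. The three pulse days would add about 0.1 month to each end date and change no conclusion.

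| Course | Start to end (month) | Scheduled visits inside | Follow-up to M24 after the course (months) |
|---|---|---|---|
| Experimental | 0 to 4 | M2, M4 | 20 |
| M2 rescue | 2.46 to 6.46 | M4, M6 | 17.5 |
| M4 rescue | 4.46 to 8.46 | M6 | 15.5 |
| M6 rescue | 6.46 to 10.46 | M9 | 13.5 |
| M9 rescue | 9.46 to 13.46 | M12 | 10.5 |
| M12 rescue | 12.46 to 16.46 | none | 7.5 (visits M18, M24) |
| M18 rescue | 18.46 to 22.46 | none | 1.5 (visit M24) |

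**Longer lag.** With 1 month instead of 14 days, the M12 course runs M13 to M17 and the M18 course M19 to M23. Still no nominal visit falls inside, and follow-up after the M18 course shrinks to 1 month.

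**Windows, M12 rescue.** With M12 held within ±1 week, the course ends between 16.23 and 16.69, before the earliest permitted M18 visit (M17). If M12 were instead given the second-year window and held at M13, the course would end at 17.46 and an M18 visit held at M17 would fall inside it.

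**Windows, M18 rescue.**
- M18 on time: end 22.46. The last visit, at M23 to M25, comes 0.54 to 2.54 months later.
- M18 held at M19: end 19 + 0.46 + 4 = 23.46. A last visit at M23 falls inside the course, and dosing continues about 0.46 month after it.

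**Contacts during rescue.** Sections 7.1 and 7.4.1 together imply three pulse-day hospitalizations, and 3.3 adds a draw on each of those days and prednisone sampling after at least 8 days. For rescued controls no examination, safety bloods or adverse-event review is specified at any of them. Nothing is specified for the rest of the oral course.

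**The case against.** The strongest reply is that the sections are compatible and safety capture does not depend on visits. Much of this stands, and it rules out several stronger readings.

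- **A reader might infer that events during late rescue are not collected.** They are. Recording is continuous over the monitored period (10.3, 10.5), and known events are followed to resolution (10.4). What follows the calendar is when collection of new events ends, and the resulting shortfall concerns M18 rescues.
- **A reader might infer that all late rescues have little follow-up.** An M12 rescue keeps about 7.5 months and two full visits.
- **A reader might infer that safety checks exist only at M2 and M4.** They are set for every visit, and compliance is discussed at each visit (5.2, 7.5). Only the steroid-specific rows of 5.4 are so limited.
- **A reader might infer that the patient is not seen at all.** The pulse days and pharmacokinetic draws are contacts. Even if equal treatment with the experimental group is read to carry over the first-day examination of 5.1, that covers the start of the course, not the months of oral treatment.
- **A reader might infer bias in a comparison of early with rescue steroids.** No such per-course comparison is planned. Both arms share one visit calendar, so extra contacts for rescued controls add ascertainment to one arm. The fix must allow for that.
- **A reader might attach a patient count.** Failure can trigger rescue from M4, 7.4.2 rules out a second course, and the background section cites about 60% non-response to RAS blockade after 3 months. Many rescues may therefore start early, and the protocol gives no split by trigger visit.

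What the reply does not remove is the gap itself: two rescue points that 7.4.1 prescribes have no scheduled follow-up visit during treatment.

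**Conclusion.** The point holds in this limited form. M12 and M18 are the only rescue points at which, on nominal dates, the full 4-month course falls between scheduled follow-up visits, and no safety assessment is tied to those courses. The consequence is less scheduled detection of examination and laboratory events in late-rescued controls. For M18 rescues, only about 1.5 months remain for new events to be captured, with an extreme in which dosing outlasts the last visit by about half a month.

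This rests on the 14-day minimum before rescue, on nominal dates except where windows are stated, and on reading 5.3 and 10.5 as giving no extension beyond M24. The number of patients affected is unknown. The primary endpoint and the sample size are not touched. It is a gap worth closing because closing it is cheap.

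**What to change.** Reconcile 5.2, 5.4 and 10.5 with 7.4.1 by amendment:

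1. Where a rescue course contains no calendar visit, tie to it the safety and steroid-compliance items already defined for follow-up visits. A telephone contact plus care bloods from private laboratories, which 5.2 already accepts, is enough.
2. Record these contacts as rescue-course assessments, so that the between-group comparison of side effects can be shown with and without them.
3. For rescue started at M18, define the end of adverse-event and serious-adverse-event collection relative to the last steroid dose, by telephone if that falls after M24.
4. Add rescue-course entries to the steroid dispensation and compliance rows of 5.4.

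The timing of the contacts and any clinical action that follows are for the sponsor and investigators.

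The cost is a protocol amendment and a few extra contacts, confined to late-rescued controls. The downside is some added ascertainment in the control arm, which is why item 2 is needed.

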3.2 Secondary objectives

The secondary objectives are:

- to evaluate the efficacy of early corticotherapy + RAS blockade (versus RAS blockade alone) at 6 and 12 months of evolution

- to compare the evolution of histological lesions between treatment groups at 12 months

- to compare the evolution of measured GFR (mGFR) between treatment groups at 12 and 24 months (or estimated GFR (eGFR) if unavailable)

- to compare the evolution of proteinuria in each group

- to compare the quality of life in each therapeutic group
- to assess the tolerance of treatment of each therapeutic group
- to identify prognosis markers of failure at 24 months
- to assess the pharmacokinetics of corticosteroids in IgA nephropathy patients
- to assess the association between corticosteroid exposure and treatment failure
- to assess the association between corticosteroid exposure and genetic polymorphisms

- to assesse the association between genetic polymorphisms and treatment failure

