7 TREATMENT ADMINISTERED TO RESEARCH PARTICIPANTS

7.1 Description of the experimental medications

For this study, two experimental medications will be administrated to the experimental group:

- 3 intravenous Methylprednisolone pulses (500 mg/pulse) will be administred during 3 successive one-day hospitalizations.
- oral corticosteroid treatment will be administred, during 4 months after the IV pulses, according to the following schedule and abacuses (see Annexe"1"):
- 1 mg/kg/d of prednisone during month 1 (begin at the D3 morning)
- 0.5 mg/kg/d of prednisone during month 2
- 0.25 mg/kg/d of prednisone during month 3
- 0.1 mg/kg/d of prednisone during month 4.

The maximum dose per day of prednisone is 80 mg.

Corticosteroids therapy is stopped at the end of the 4th month.

Corticosteroids dosage is rounded down to the closest multiple of 5 mg.

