7.4.2. Prohibited treatments

No treatments are prohibited, except from those contra-indicated with the use of corticosteroids (cf SmPC). A patient have already received a corticosteroid treatment, he should not receive a new corticotherapy.

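### SF36 is collected only at M12 and M24, so quality of life has no baseline score and no measurement during the experimental arm's steroid course

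*Protocol*

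**What the plan says.** Protocol section 3.2 sets as a secondary objective "to compare the quality of life in each therapeutic group". Section 4.1.2 makes this operational as "Comparison of life quality scale in each therapeutic group with SF36 scale at 12 and 24 months". Section 5.2 schedules the instrument in the same way ("at the visit M12 and M24, SF36 scale and biological collection (blood and urine"), and the tables in sections 5.4 and 5.5 agree. The inclusion and D0 procedures in section 5.1 contain no SF36.

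On steroid exposure, section 7.1 starts the experimental course at D0 and states: "Corticosteroids therapy is stopped at the end of the 4th month". Section 7.4.2 rules out a second course: "A patient have already received a corticosteroid treatment, he should not receive a new corticotherapy".

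Controls can receive the same 4-month course later. Section 7.4.1 allows it after M2 for rapid loss of renal function and leaves it optional after M4 ("At 4 months, rescue corticosteroid treatment (4 months of treatment, same protocol of experimental group) could be administred in case of failure"). At later visits it is expected on failure: "At 6, 9, 12, or 18 months, rescue corticosteroid treatment (4 months of treatment, same protocol of experimental group) should be administred". In each case the values are first rechecked "on a second sample, within an interval of at least 14 days".

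**The concern.** The two strategies differ mainly in when, and whether, a patient takes steroids. Section 2.2 itself describes steroids as capable of serious side effects. A reader would expect the quality-of-life data to show what the early course costs patients while they take it. The schedule omits that period entirely.

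There is also no score from before randomisation. SF36 therefore cannot be analysed as change or adjusted for its starting value, whereas GFR and proteinuria both have baselines and are analysed as change (sections 4.1.2 and 9.2). A baseline would also help with missing scores. Under section 5.7.3.1, patients who reach ESRD or are transplanted have no further protocol visits. If that happens before M12, the patient contributes no SF36 at all, and there is no earlier value to inform the analysis.

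This is a question of data collection. An analysis plan may choose any covariate it likes, but it cannot recover scores that were never taken.

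**Working it through.** **Inputs.** From the protocol: SF36 at M12 and M24 (4.1.2, 5.2, 5.4, 5.5); experimental steroids from D0 to M4 (7.1); rescue triggers at M2, M4, M6, M9, M12 and M18, with a recheck after at least 14 days and a 4-month course (7.4.1); visit windows of ±1 week in year 1 and ±1 month in year 2 (5.4); 61 patients per group (9.1). Assumed: the correlation ρ between a baseline and a follow-up SF36 score, which the protocol does not give, shown over 0.3 to 0.7; no missing data.

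**The plan's own figure.** The protocol gives no sample size, SD or target difference for SF36. Its 61 per group is for the primary endpoint (60% against 35% failure, 80% power, two-sided 5%). The pooled normal approximation gives 62 and the arcsine formula 61.3, so 61 is reproduced closely enough and is used as n below.

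**Step 1: distance from the experimental course.** First SF36: 12 − 4 = 8 months after steroids end. Second: 24 − 4 = 20 months. None of the two assessments falls within D0 to M4.

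**Step 2: who is on protocol steroids at an SF36 visit.** Earliest start = trigger visit + 14 days (about 0.46 month); end = start + 4 months.

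| Control rescue triggered at | Course runs about | On steroids at M12? | On steroids at M24? |
|---|---|---|---|
| M2 | M2.5 to M6.5 | no | no |
| M4 | M4.5 to M8.5 | no | no |
| M6 | M6.5 to M10.5 | no (ended 1.5 months before) | no |
| M9 | M9.5 to M13.5 | **yes** | no |
| M12 | M12.5 to M16.5 | no (starts after) | no |
| M18 | M18.5 to M22.5 | no | no (ended 1.5 months before) |

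The 14 days are a minimum, so longer delays shift these courses later. At M24 an overlap is possible at the edge of the windows: an M18 visit one month late gives an end near M23.5, and an M24 visit one month early falls at M23. Experimental patients are not re-treated, so on schedule none of them is on protocol steroids at either assessment.

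**Step 3: precision lost by having no baseline.** In SD units, the difference detectable at 80% power is (1.96 + 0.84) × √(2/61) = 0.51, and the 95% CI half-width is 1.96 × √(2/61) = 0.35. With the baseline as covariate the variance is multiplied by 1 − ρ², so both figures are multiplied by √(1 − ρ²). The equivalent sample is 61/(1 − ρ²) per arm.

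| ρ (assumed) | Variance left, 1 − ρ² | Variance cut, ρ² | Detectable difference (SD) | CI half-width (SD) | Equivalent n per arm | Extra patients, 1/(1 − ρ²) − 1 | Power at 0.4 SD |
|---|---|---|---|---|---|---|---|
| no baseline | 1.00 | none | 0.51 | 0.35 | 61 | none | 60% |
| 0.3 | 0.91 | 9% | 0.48 | 0.34 | 67 | 10% | 64% |
| 0.5 | 0.75 | 25% | 0.44 | 0.31 | 81 | 33% | 72% |
| 0.7 | 0.51 | 49% | 0.36 | 0.25 | 120 | 96% | 87% |

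**The case against.** The protocol is consistent with itself here: four places say M12 and M24, and that is what is collected. Its rationale is a long-lasting benefit of early treatment (section 2.3), so late quality of life is a coherent target. Early harm is not unobserved either. Tolerance is a separate objective, side effects are compared by arm, and section 10.3 requires all adverse events to be recorded. All of this stands. What is absent is the patient-reported measure in that period, and a starting score.

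Two stronger readings are tempting, and the documents support neither.

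- A reader might infer that the comparison is biased in favour of early steroids. It is not biased for what it estimates. Deferred steroids on failure are part of the control strategy as section 4.2.1 defines it, so a rescued control's M12 score is a genuine consequence of assignment. Randomisation protects the M12 and M24 comparisons without a baseline.
- A reader might infer that the data can show only the control arm's steroid burden. That holds only for burden while on treatment, and nominally only for M9 rescues at M12. Those are patients not already treated after an earlier visit. The protocol does not give their number, and they are in the third month of a tapering course by then. Lasting harms, such as the diabetes and fractures named in section 10.3, and disease-related quality of life can appear in both arms.

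The precision gain also rests on an assumed correlation. A baseline would precede the scores by 12 and 24 months, so a value as low as 0.3, with its 9% saving, cannot be excluded.

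**Conclusion.** The point holds in a limited form. The quality-of-life objective has no baseline score and no measurement during the experimental steroid course, and no later analysis can repair either gap.

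The M12 and M24 comparisons are valid but less precise than they could be. With 61 per arm and complete data the 95% CI half-width is about 0.35 SD; with a baseline covariate it would be 0.34, 0.31 or 0.25 SD at correlations of 0.3, 0.5 or 0.7. The protocol supplies no correlation, so only the range can be claimed.

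A null SF36 result at M12 and M24 should not be read as showing that early steroids cost patients nothing in quality of life, because the period in which they are taken is not sampled.

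This is one of eleven secondary objectives, no power is claimed for it, and the primary endpoint and sample size are untouched. It is a minor-to-moderate improvement, worth making because it is cheap.

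**What to change.** Add two SF36 assessments in both arms.

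1. **Inclusion visit, after consent and before randomisation.** Consent and randomisation take place at the same visit and the trial is open-label, so the order must be written down: a score given after allocation is known is not a clean baseline.
2. **The existing M2 visit.** It lies mid-course for the experimental arm. The earliest rescue starts about two weeks after the M2 visit, so no control should yet be on protocol steroids. M4 serves less well: with a ±1 week window it catches the last step of the taper or patients already off treatment, and a control rescued after M2 could be mid-course.

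Compare SF36 at M2, M12 and M24 with the baseline score as a covariate, and say in section 4.1.2 that M2 describes quality of life during treatment while M12 and M24 describe later quality of life under each strategy.

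The cost is two self-completed questionnaires at visits that already take place, an e-CRF page and a small amendment. Patients already enrolled would lack a baseline, so the benefit shrinks the later the change is made.
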